All information concerning the study device supplied by Fundación Investigación HM Hospitales in connection with this study, and not previously published, is considered confidential and proprietary information. This information includes the clinical investigation plan, subject informed consent and case report forms. This confidential information shall remain the sole property of Fundación Investigación HM Hospitales, shall not be disclosed to others without prior written consent from Fundación Investigación HM Hospitales and shall not be used except in the performance of this study.

The information developed during the conduct of this clinical study is also considered confidential and will be used by Fundación Investigación HM Hospitales in connection with the development of the study device. This information may be disclosed as deemed necessary by Fundación Investigación HM Hospitales.

The below-named individuals are authorized to sign this clinical investigation plan and its amendments.

_____ / _____ / _____

Signature

Date

Printed Name

Title

1. - SUMMARY

1. Study Title:	Epidural Pulsed Radiofrequency versus Epidural Steroids Injection for Treatment of Failed Back Syndrome: A Prospective, Randomized, Single-Blind and Multicenter Study
2. Sponsor:	Fundación Investigación HM Hospitales
3. Type of Clinical Investigation:	Clinical Investigation with CE-marked medical devices.
4. Coordinating Investigator:	[name] [name], MD PhD.
5. Protocol Code:	EPIPUL
6. Geography	Spain
7. Clinical Sites:	
Hospital Universitario Puerta de Hierro (Madrid, Spain).Hospital Universitario Rey Juan Carlos (Madrid, Spain).Hospital Universitario de Sanchinarro (Madrid, Spain)Hospital Fremain Majadahonda (Madrid, Spain)Hospital Universitario La Fé (Valencia, Spain)Hospital Clínico Universitario de Santiago (Santiago de Compostela, Spain)
8. Study Purpose:	The present pilot study suggests that the epidural application of PRF to the dorsal roots and proximal DRG can be safe and effective in the treatment of intractable pain after back surgery. Several explanatory hypotheses motivate further study of this apparent improvement over transforaminal PRF, which has produced inconsistent results in published reports to date.
9. Treatments	Experimental Group (62 patients): Epidural radiofrequency by catheter in the epidural space plus steroids administration. Control Group (62 patients): Epidural steroids injection.
10. Primary Endpoint:	Difference in pain reduction between the control group and the experimental group since the baseline visit and the 6 month visit evaluated by Visual Analogue Scale (VAS).
11. Secondary Endpoints:	
Change from Baseline in pain at 1, 2 and 4 months (Visual Analogue Scale, VAS).Change from Baseline in disability at 1, 2 and 6 months (assessed by Oswestry Disability Index, ODI).Change from Baseline in health survey at 1, 2, 4 and 6 (assessed by Short Form Health Survey, SF-12).Change from Baseline in neuropathic pain at 1, 2 and 6 months (assessed by Douleur Neuropathique 4 Questions, DN4).Change from Baseline in improvement of pain at 1, 2, 4 and 6 months (assessed by Patient Impression of Improvement, PGI-I).Assessment of subject satisfaction with experimental procedure 2 and 6 months.Incidence of unanticipated adverse device effects.Change in opioid intake in 6 months.Adverse events related to procedures (experimental group and control group).
12. Study Design:	Prospective, randomized, single-blind and multi-centre study. Controlled comparison between epidural steroids injection with catheter and epidural radiofrequency by catheter in the epidural space plus steroids administration. After the treatment, patients will be followed-up at 1, 2, 4 and 6 months.

	
Inclusion Criteria:
 
1. Men and women over 18 years old.2. Written informed consent according to ICH/GCP and Spanish legislation, obtained before any study procedure.3. Pain VAS score at least 5 points.4. Duration of pain at least 3 months after back surgery with conservative treatment.5. Leg-dominant radicular pain deemed neuropathic based on clinical history and examination.6. Responsive to selective radicular nerve block (bupivacaine 0.125%).7. Patients who have had a previous epidural steroid injection. 
Exclusion Criteria:
 
1. Pregnancy or lactation.2. Inability to give informed consent in the absence of a legal representative.3. Subjects that are participating in a study with medicines or other clinical devices.4. Those who show inability to follow the instructions or collaborate during the development of the study.5. If in the opinion of the researcher there are findings in the physical examination, abnormalities in the results of the clinical analyses or other medical, social or psychosocial factors that could have a negative influence.6. Patients with myelopathy, systemic diseases, infection (systemic or local), cancer, indication for immediate surgery, coagulation disorders, use of anticoagulants, diabetes mellitus or multiple sclerosis.7. Life expectancy of less than one year.8. A current diagnosis of a progressive neurological disease.
14. Study Population:	Patients with chronic lumbar radicular pain following failed back surgery.
15. Sample Size:	62 patients per group, a total of 124 patients.
16. Research Ethics Committee:	CEIm HM Hospitales
17. Calendar:	
The total duration of the study from first enrolment to last subject last visit is estimated to be 28 months:
 
• 4 months to prepare all documentation for contracts and Committee approval.• 12 months for enrolment.• 6 months follow up.• 6 months to close the investigation and provide final study report.

2. – INDEX

1. - SUMMARY	3
2. – INDEX	5
3. - GENERAL INFORMATION.....	7
3.1 Clinical Investigation Identification	7
3.2 Type of Study.....	7
3.3 Description of the Device Study.....	7
3.4 Data Related to the Sponsor	7
3.5 Monitor Identification	7
3.6 Information on the Investigator Team	7
3.7 Expected Duration of the Clinical Investigation	7
3.8 Data Safety Monitoring Board (DSMB)	8
4. - JUSTIFICATION.....	8
5. - HYPOTHESIS AND ENDPOINTS	10
5.1 Hypothesis.....	10

3.1 Clinical Investigation Identification

Protocol Code: EPIPUL

Title of the Clinical Investigation: Epidural Pulsed Radiofrequency versus Epidural Steroids Injection for Treatment of Failed Back Syndrome: A Prospective, Randomized, Single-Blind and Multicenter Study.

3.2 Type of Study

Clinical trial with a CE marked Medical Device used within its intended purpose and according to its authorized indications.

3.3 Description of the Device Study

- 3.3.1. RCE Introducer Cannulae (RCE-C916S-P).
- 3.3.2. RCE 40 cm Electrodes (RCE-E401519-P).
- 3.3.3. G4 RF Generator (RFG-4-120 V).
- 3.3.4. Disposable Ground Pads (DGP-PM-10).
- 3.3.5. Voltage Controlled Injection Electrode. Length 10 cm / Tip 5 mm / Echo RF (CR-10-P).

3.5 Monitor Identification

Monitor to be assigned by the Sponsor.

3.6 Information on the Investigator Team

See Annex I.

3.7 Expected Duration of the Clinical Investigation

The overall duration of the study will be twenty-eight months, one year of recruitment and six months of follow-up, from the inclusion of the first patient until the last follow-up visit of the last patient.

3.8 Data Safety Monitoring Board (DSMB)

A Data Safety Monitoring Board (DSMB), independent from the EPIPUL consortium, will be appointed to perform an independent supervision of the safety aspects of the study. The DSMB will have 3 members including at least one expert in clinical trial methodology and statistics, and one pain management expert independent from the study team. The DSMB will be established before the start of the study and will follow the procedures established in the “DSMB Charter for the EPIPUL study”.

4. - JUSTIFICATION

Over the last twenty years, Pulsed Radiofrequency (PRF) has been applied to nerves as a less destructive alternative to thermal RF ablation (RFA) for pain reduction without disruption of somatic sensation and motor function¹. PRF delivers RF in bursts that expose a target nerve to high-intensity electric fields (E-fields) but avoids gross thermal ablation by allowing electrically-generated heat to dissipate between bursts. Though the mechanism of PRF has not yet been fully established, theoretical and experimental findings suggest that the RF electric-field induces moderately disruptive^{2, 3, 4, 5, 6, 7, 8} and neuromodulatory effects in primary sensory neurons and dorsal horn^{2, 3, 7, 9, 10, 11, 12, 13, 14, 15, 16} that can reduce neuropathic hyperalgesia/allodynia^{14, 15, 16, 17, 18, 19, 20, 21, 22}. Clinically, PRF is often applied using a “transforaminal” approach whereby a sharp RF cannula/electrode is positioned near a DRG and/or spinal nerve via the neural foramina. Transforaminal PRF of the DRG has been used for treatment of cervical radicular pain^{23, 24, 25}, lumbar radicular pain^{24, 26, 27, 28, 29}, postsurgical thoracic pain^{26, 30}, stump pain³¹, postsurgical ilioinguinal neuralgia³², and other pain disorders. PRF has also applied to the suprascapular nerve for shoulder pain^{33, 34, 35}, the saphenous³⁶ or sciatic nerves³⁷ for knee pain, the obturator and femoral nerves for hip pain³⁸, the genitofemoral or ilioinguinal or iliohypogastric nerve for groin pain or orchialgia³⁹, the lateral femoral cutaneous nerve for meralgia paresthetica⁴⁰, the intercostal nerve for postherpetic neuralgia⁴¹, the Gasserian ganglion for trigeminal neuralgia⁴², the greater and lesser occipital nerves for occipital neuralgia^{43, 44}, a stump neuroma for phantom limb pain⁴⁵, and other peripheral targets.

Failed Back Surgery Syndrome (FBSS) refers to a diverse array of chronic back or leg pain disorders that are either caused or untreated by a previous back surgery^{46, 47, 48}. FBSS can involve multiple nociceptive and neuropathic pain etiologies for each patient, including internal disc disruption, facet and sacroiliac joint syndromes, structural instability, spondylitis, radiculitis, disc herniation, neural or spinal foramina stenosis, arachnoiditis, epidural and other postsurgical fibrosis, and other disorders. Whether due to FBSS inherent heterogeneity, multisegmental involvement or lack of specific diagnostic criteria, FBSS pain can be challenging to treat. Epidural steroids injection is currently the most common treatment for FBSS while transforaminal PRF

of the DRG and epidurolysis has produced mixed results^{26, 27}. The present study explores the hypothesis that treatment of FBSS pain can be improved by epidural application of PRF to the DRG and dorsal nerve root, thereby reducing or blocking ectopic pain signals originating from sites of dorsal root irritation within the spine^{49, 50, 51}, in addition to ectopia from the DRG^{49, 52, 53, 54, 55} and nociceptive signals from other painful anatomy. This study also explores the concept that epidural access can facilitate treatment of all affected dorsal roots and DRGs, some of which may be inaccessible transforaminal due to implanted hardware and bone anatomy.

Insausti et al. previously presented case reports about Epidural Radiofrequency with Catheter (ERC), wherein pulsed RF was delivered to lumbosacral nerve roots using an epidurolysis catheter inserted through the sacral hiatus without temperature control⁵⁶. More recent case reports describe a similar technique using a catheter electrode that is specifically designed and indicated for radiofrequency treatment, and that includes a temperature sensor, an elongated 15-mm active tip, a generator connection, and an injection port (RCE-E401519-P, Cosman Medical, Inc., Burlington, MA, USA)^{57,58}. Temperature monitoring was used to limit the risk of exposing spinal nervous tissue to neurolytic temperatures, and to maximize the electric-field dose (E-dose) under the 42 °C safety limit^{3, 13, 59}. A longer active tip was used to increase the theoretical likelihood of placing the electrode active tip nearby the target nerve, and thus, of exposing that nerve to sufficiently strong E-fields.

The epidural orientation of the affected nerve roots may be particularly useful for PRF treatment of any pain syndrome involving direct irritation of DRG, including FBSS. Mechanical, chemical or ischemic nerve injury can cause ectopic firing that originates from both the site of injury and the DRG^{51, 63}. While PRF is theorized to induce pain-relieving changes in the DRG and dorsal horn, structural and functional experiments also suggest that PRF may relieve pain at least in part using blockage of action potential propagation along smaller-diameter axons^{4, 7}. Consistent with this, PRF is generally applied between the spinal cord and the site of a nerve injury when used to treat neuropathic pain caused by peripheral nerve damage. It can be reasonably hypothesized that treatment of pain involving nerve dysfunction within the spine would be improved by PRF application to the epidural nerves in epidural space before DRG is formed, so that pain signals generated in the central axon (dorsal root), soma (DRG), and peripheral axon (peripheral nerve) of afferent neurons are all blocked from entering the central nervous system.

Even if neuropathic pain is initiated only at a peripheral location, the application of PRF closer to the DRG has been associated with better outcomes³⁰, perhaps due to cessation or blockage of painful ectopic discharge emanating from the DRG in neuropathy⁶³. Provided that the spinal canal is not itself restricted, epidural electrode placement can improve the positioning of the electrode active tip near the DRG, particularly at spinal levels that are inaccessible transforaminal due to implanted hardware, osteophytes overgrowth, or normal vertebral anatomy. Dorsal

roots and epidural nerves are organized somatotopically within the spinal canal ⁶⁴, and each DRG is located at a regular position relative to the pedicle ⁶⁵ which can be readily visualized radiographically relative to a radiopaque catheter electrode.

The PRF electric field strength decreases with distance from the electrode and across the width of a target nerve, so the relative position of a PRF electrode and target nerve likely affects efficacy ³. Epidural placement may enhance nerve targeting and exposure to E-fields by tending to orient the side of the electrode active tip across the nerve ^{3, 65}, by allowing for use of a longer active tip (eg 15 mm epidurally vs. 5-10 mm transforaminal), and by avoiding physician hesitance to insert a sharp cannula deep into the neural foramina or near critical blood vessels ³⁰. The epidural approach also facilitates the treatment of pain disorders with multisegmental and bilateral involvement, by providing for targets of multiple spinal nerves through a single needle insertion. In contrast, the transforaminal approach requires a separate needle to be placed at each spinal level and side.

Differences in patient selection and methods from the previous study of transforaminal PRF ²⁷ could also account for the apparent superiority of epidural over transforaminal PRF for the treatment of FBSS pain. In a previous study, PRF applied at each DRG for 120 seconds was unsuccessful in consistently reducing FBSS pain ²⁷. In the present study, PRF was applied at each level for 480 seconds. This longer treatment time likely increased the duration for which target nerves were exposed to the PRF electric field and could explain improved outcomes.

Temperature control is important for safe and effective application of PRF in the epidural space. Though no complications were reported during voltage-controlled epidural PRF ⁵⁶, inadvertent exposure of nervous structures within the spinal canal to neurolytic temperatures could produce substantial complications. Temperature control also enables the delivery of the maximal pulsed RF electric field intensity and duration under the safety temperature limit of 42 °C ⁵⁹, which was associated with greater pain reduction in a rat neuropathic pain model than was PRF delivery at 37 °C ¹³. In the absence of temperature control, PRF efficacy may be limited by the need to preemptively moderate PRF parameters so that neurolytic temperatures are avoided under a wide variety of tissue conditions, electrode sizes, and patients ⁵⁹. These factors can vary greatly, as evidenced by our comparison of impedance and current measurements from small transforaminal electrodes and larger epidural electrodes.

5. - HYPOTHESIS AND ENDPOINTS

5.1 Hypothesis

This clinical investigation will intends to demonstrate reduction of chronic lumbar radicular pain following back surgery by epidural application of temperature-

controlled PRF to the dorsal radicular filaments proximal to the DRG and dorsal nerve root in the epidural space using a guidable, radio-opaque, catheter electrode (Boston Scientific RCE) having an elongated 15-mm active tip and a temperature sensor at its rounded distal point (Cosman RCE-E401519-P) versus epidural steroids injection.

5.2 Primary Endpoint

Difference in pain reduction between the control group and the experimental group since the baseline visit and the 6 month visit evaluated by Visual Analogue Scale (VAS).

5.3 Secondary Endpoints

- 5.3.1. Change from Baseline in pain at 1, 2 and 4 months (assessed by Visual Analogue Scale, VAS).
- 5.3.2. Change from Baseline in disability at 1, 2 and 6 months (assessed by Oswestry Disability Index, ODI).
- 5.3.3. Change from Baseline in health survey at 1, 2, 4 and 6 months (assessed by Short Form Health Survey, SF-12).
- 5.3.4. Change from Baseline in neuropathic pain at 1, 2 and 6 months (assessed by Douleur Neuropathique 4 Questions, DN4).
- 5.3.5. Assessment of improvement of pain with experimental procedure at 1, 2, 4 and 6 months (assessed by Patient Impression of Improvement, PGI-I).
- 5.3.6. Incidence of unanticipated adverse device effects.
- 5.3.7. Change in opioid intake in 6 months.
- 5.3.8. Adverse events related to procedures (experimental group and control group).
- 5.3.9. Assessment of subject satisfaction with experimental procedure at 2 and 6 months.

6. - ELIGIBILITY CRITERIA

6.1 Inclusion Criteria

1. Men and women over 18 years old.
2. Written informed consent according to ICH/GCP and Spanish legislation, obtained before any study procedure.
3. Pain VAS score at least 5 points.
4. Duration of pain at least 3 months after back surgery with conservative treatment.
5. Leg-dominant radicular pain deemed neuropathic based on clinical history and examination.
6. Responsive to selective radicular nerve block (bupivacaine 0.125%).
7. Patients who have had a previous epidural steroid injection.

6.2 Exclusion Criteria

1. Pregnancy or lactation.
2. Inability to give informed consent in the absence of a legal representative.
3. Subjects that are participating in a study with medicines or other clinical devices.
4. Those who show inability to follow the instructions or collaborate during the development of the study.
5. If in the opinion of the researcher there are findings in the physical examination, abnormalities in the results of the clinical analyzes or other medical, social or psychosocial factors that could have a negative influence.
6. Patients with myelopathy, systemic diseases, infection (systemic or local), cancer, indication for immediate surgery, coagulation disorders, use of anticoagulants, diabetes mellitus or multiple sclerosis.
7. Life expectancy of less than one year.
8. A current diagnosis of a progressive neurological disease.

7. - STUDY DESIGN

7.1 Type of Clinical Investigation

Prospective, randomized, single-blind and multi-center study.

Controlled comparison between epidural and transforaminal electrode placement and epidural steroids injection.

7.2 Randomization Process

The clinical investigation will be single-blind. The assignment to the type of surgical treatment is carried out randomly and open for the investigators but not for

the patients. Randomization will be done with concealment of the randomization sequence and it takes place after informed consent has been signed.

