7.5.2. Baseline* (within 30 days from Screening Visit)

At this clinic visit the subject will undergo the following evaluations:

- Randomization.
- Eligibility criteria will be re-evaluated.
- Any change of medication will be collected.

- Subjects will be asked to fill out standard questionnaires to assess (VAS, ODI, SF-12 and DN4).
- Subjects will be assessed for possible adverse events, if any.
- AP and lateral view lumbar imaging.
- Screening failures will be collected.

*Baseline and Treatment visits could be at the same time.

All applicable information will be documented on a CRF.

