7.5.3. Treatment Visit (\pm 15 days)

At this clinic visit the subject will undergo the following evaluations:

- Treatment process.
- Study completion (if applicable).
- Adverse event monitoring.
- Deviation monitoring.
- Any change of medication will be collected.

7.5.4. 1 Month Visit (\pm 7 days)

At this clinic visit the subject will undergo the following evaluations:

- Any change of medication will be collected.
- Subjects will be asked to fill out standard questionnaires to assess (VAS, ODI, SF-12, DN4 and PGI-I).
- Subjects will be assessed for possible adverse events, if any.
- Adverse event monitoring.
- Deviation monitoring.

All applicable information will be documented on a CRF.

7.5.5. 2 Months Visit (\pm 14 days)

At this clinic visit the subject will undergo the following evaluations:

- Any change of medication will be collected.
- Subjects will be asked to fill out standard questionnaires to assess (VAS, ODI, SF-12, DN4 and PGI-I).
- Subjects will be assessed for possible adverse events, if any.
- Adverse event monitoring.
- Deviation monitoring.
- Subject questionnaire of treatment satisfaction.

All applicable information will be documented on a CRF.

7.5.6. 4 Months Visit (\pm 14 days)

At this clinic visit the subject will undergo the following evaluations:

- Any change of medication will be collected.
- Subjects will be asked to fill out standard questionnaires to assess (VAS, SF-12 and PGI-I).
- Subjects will be assessed for possible adverse events, if any.
- Adverse event monitoring.
- Deviation monitoring.

All applicable information will be documented on a CRF.

7.5.7. 6 Months Visit (\pm 20 days)

At this clinic visit the subject will undergo the following evaluations:

- Any change of medication will be collected.
- Subjects will be asked to fill out standard questionnaires to assess (VAS, ODI, SF-12, DN4 and PGI-I).
- Subjects will be assessed for possible adverse events, if any.
- Adverse event monitoring.
- Deviation monitoring.
- Subject questionnaire of treatment satisfaction.

All applicable information will be documented on a CRF.

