The Sponsor contact information for these events is:

[name] [name],

E-mail: [contact]

Table1. Schedule

Assessment								
Visit	Screening	Baseline	Treatment	1 month	2 months	4 months	6 months	Unscheduled
Window		Within 30 days from screening	± 15 days	± 7 days	± 14 days	± 14 days	± 20 days	
Pregnancy Test	X							
Sign Informed Consent	X							
Entry Criteria Evaluation	X	X						
Demographics	X							
Medical History	X	X						
Randomization		X						
Treatment Process			X					
Pain and Surgical History	X							
Medication Usage	X		X	X	X	X	X	X
VAS questionnaire		X		X	X	X	X	X
ODI questionnaire		X		X	X		X	X
SF-12 questionnaire		X		X	X	X	X	X
DN4 questionnaire		X		X	X		X	X
PGI-I questionnaire				X	X	X	X	X
Subject questionnaire of treatment satisfaction					X		X	X
AP and Lateral radiography imaging		X						
Deviation Monitoring			X	X	X	X	X	X
Adverse Event Monitoring		X	X	X	X	X	X	X
Screening Failures		X						
Study Completion			X				X	X

9. - TREATMENT DESCRIPTION

Both treatments (control group and experimental group) will always be performed in an ambulatory environment through sedation and anaesthesia.

The lower back and buttocks will be prepared for an aseptic technique. Lateral and AP views of the sacral foramina and hiatus will be taken and the entry point for the epidural needle will be marked on the surface of the skin, 1-2 cm caudal to the sacral hiatus. The skin and subcutaneous tissue underlying the entry site will be anesthetized using 1-2 ml of 1% lidocaine.

A 9-cm-long, 16-gauge (ga) epidural needle (Cosman RCE-C916S-P) is inserted through the skin and into the caudal canal, 1-2 cm beyond the sacral hiatus, ending at an angle of approximately 15° concerning the skin. Intravascular and subdural placement will be ruled out by injecting 1-1.5 ml of non-ionic radiographic contrast (180 mg of iohexol per ml) through the fluoroscopic needle *in vivo*.

9.1 Control Group. Epidural Steroids Injection.

A radiopaque, guidable radiofrequency electrode (Cosman RCE-E401519-P) will bend slightly at a 45° angle proximal to its metal tip and then be inserted through the needle. The electrode shall include an active 20/15 mm gauge tip, a 19/40 cm gauge shaft, a rounded distal point temperature sensor, an injection port and an integral generator connection. The electrode will be visualized by fluoroscopy as it is guided in the epidural space from the sacral canal to the lumbar vertebral canal.

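### Randomisation sits at Baseline and is open to investigators, with nothing withholding the arm until the access steps shared by both arms are done, so cancelled or failed access can leave the analysis differently by arm

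*Combined protocol and SAP*

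**What the plan says.** **Who knows the arm.** Section 7.2: "The assignment to the type of surgical treatment is carried out randomly and open for the investigators but not for" the patients. The sequence is concealed. The section's only timing rule for randomisation is that "it takes place after informed consent has been signed".

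**When.** Section 7.5.2 and Table 1 put randomisation at Baseline. In 7.5.2 it is the first item, ahead of "Eligibility criteria will be re-evaluated" and the questionnaires. Treatment is a separate visit with a window of ±15 days (7.5.3), although "Baseline and Treatment visits could be at the same time". Study completion, where applicable, is among the items of the Treatment visit.

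**What the arms share.** The introduction to section 9 describes the 16-gauge caudal needle and its contrast check once, for both arms. Sections 9.1 and 9.2 then contain the same sentence: "The electrode will be visualized by fluoroscopy as it is guided in the epidural space from the sacral canal to the lumbar vertebral canal". Both connect the electrode to the same generator and a ground pad. Only after that do they part. The control arm has zero voltage for 240 seconds and betamethasone. The experimental arm has tip placement at each level, stimulation and PRF.

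**Who is analysed.** Section 7.10 limits ITT to subjects who received a study treatment. ITT-B covers everyone who completes the baseline assessment, but its stated purpose is adverse-event capture. Section 13 does not name the population for the primary test.

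**The concern.** Sequence concealment protects the decision to enrol. It does not protect what is done once the arm is known. Between randomisation and the point where the arms diverge, the plan leaves room for three decisions by someone who may know the arm: to cancel before treatment, to persist with difficult access, or to abandon it. None of the shared steps needs the allocation to be known.

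The population definition is what makes this matter. A randomised patient in whom access is abandoned, and who receives no treatment, is outside the set labelled ITT. If such decisions differ by arm, the groups compared are no longer the groups randomised, and a larger sample does not repair that. Even if failures were equal in both arms, they would cost power: through fewer evaluable patients if excluded, or through a diluted difference if kept.

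The order of items in 7.5.2 adds a smaller gap of the same kind. If it is followed literally, the eligibility re-check comes after randomisation, and exclusion criterion 5 rests on the researcher's opinion.

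**Working it through.** **1. The plan's own figure (7.3).** Inputs: two-sided t-test at 5%, power 90%, means 40 and 60 mm (difference 20 mm), SD 30 mm, losses 20%. With the noncentral t distribution, 49 per group gives power 0.904 (48 gives 0.898). Then 49/0.8 = 61.25, rounded up to 62. The stated 62 per group is reproduced, and this point disputes no figure in 7.3. Expected evaluable per group: 62 × 0.8 = 49.6, about 50.

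**2. Assumed input.** The documents give no access-failure rate f and do not break down the 20% losses. I assume f = 5% to 10%, which is 124 × 0.05 = 6.2 to 124 × 0.10 = 12.4 patients.

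**3. Failures kept in the PRF arm with no PRF effect.** The expected difference becomes 20 × (1 − f). The noncentrality is difference / (30 × √(2/50)) = difference / 6, on 98 degrees of freedom. SD is held at 30 mm.

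| f | Difference (mm) | Noncentrality | Power, 50 per arm |
|---|---|---|---|
| 0 | 20 | 3.33 | 0.910 |
| 5% | 19 | 3.17 | 0.880 |
| 10% | 18 | 3.00 | 0.844 |

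**4. Failures excluded equally from both arms, on top of the 20% losses.** Evaluable per arm = 49.6 × (1 − f): 49.6, 47.1 and 44.6 for f = 0, 5% and 10%. Power at 20 mm: 0.908, 0.893 and 0.876.

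**5. Failures excluded unequally.** This is an illustration of mechanism only; every input is assumed. There is no true effect. In each arm 15% of patients have difficult access and a 6-month change D mm worse than the rest. One arm excludes 10% of its patients, all from that subgroup; the other excludes none. Relative to patients with easy access, an arm's mean is −D × (0.15 − f)/(1 − f).

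- D = 20: −20 × 0.05/0.90 = −1.11 against −20 × 0.15 = −3.00, a spurious difference of 1.89 mm. With SE = 30 × √(2/49) = 6.06 mm, the two-sided type I error is about 0.061.
- D = 30: −1.67 against −4.50, a spurious difference of 2.83 mm; type I error about 0.075.

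**6. Recruitment cost of later release.** If failed access precedes randomisation, the number starting the procedure is 124/(1 − f): 124/0.95 = 130.5, so 131; 124/0.90 = 137.8, so 138. That is 7 to 14 more patients than 124.

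**The case against.** **The moment of release is inferred.** No section says when the operator learns the arm. The documents say only that assignment is open to investigators and made at Baseline, with no later release step. This stands, so the point is worded as what the plan permits.

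**The control arm also has to gain access.** A reader might infer that a control-arm operator needs only an epidural injection and can stop early. Section 9.1 does not support that: it requires the same electrode to be guided to the lumbar canal, the generator to be connected, contrast to be injected through the electrode and betamethasone then given. Differing effort is possible, but stopping short would depart from the written procedure.

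**Access failure is not documented.** Section 4 lists stenosis and epidural fibrosis among the conditions in this population, and makes one advantage of epidural placement conditional on an unrestricted canal. It does not say that the catheter may fail to advance, and it presents the epidural route as improving access. The failure rate is my assumption, and the planned 20% losses may already cover some of these patients.

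**Cancellation is a narrow route.** Patients are blind, so only investigator-driven cancellation can depend on arm, and a same-day Baseline and Treatment shortens the interval. Study completion at the Treatment visit is a visit item that also appears for unscheduled visits, not a rule for failed access. Even on one day, though, nothing ties release of the arm to completed access.

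**Moving randomisation is only a partial cure.** Placement at each level and the stimulation criteria in 9.2 come after the proposed release, so PRF-only failures remain. Analysing all randomised patients would deal with differential exclusion without moving randomisation. That is right, and the fix therefore includes it. It would not remove the arm-aware conduct of the shared steps, which only later release addresses.

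**Conclusion.** The point holds as a permitted and avoidable route to bias, not as a demonstrated one. The text establishes randomisation at Baseline, assignment open to investigators, shared access steps in both arms, no step that withholds the arm until those are complete, and an ITT set restricted to treated subjects. That the operator knows the arm during access is an inference from these.

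Under an assumed failure rate of 5% to 10%, with failures kept in the PRF arm without PRF effect, power with 50 per arm falls from 0.91 to between 0.88 and 0.84. If failures are excluded equally it falls from 0.908 to between 0.893 and 0.876. The arm-dependent bias cannot be sized from the documents; the 1.9 and 2.8 mm shifts only show how it would arise.

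A reader might infer that the trial will be biased, or that later release would remove all procedural failures from the randomised comparison. The documents support neither. The change is worth making because it is cheap and changes neither treatment.

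**What to change.** 1. **Sections 7.2, 7.5.2, 7.5.3 and Table 1:** move randomisation to the Treatment visit, after the eligibility re-evaluation and the baseline questionnaires.
2. **Section 9:** state that the concealed allocation is released only once the shared needle insertion and its contrast check, guidance of the electrode to the lumbar canal, and connection of the generator and pad are done. Release it silently (sealed envelope or web system), so that the patient stays blind. Record failures before this point, with the reason, as not randomised.
3. **Section 7.10 and section 13:** make all randomised subjects, in their assigned arm, the primary analysis population. PRF-specific placement or stimulation failures after release then stay in the PRF arm.

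**Cost.** Wording only in the protocol, with no extra device, since both arms already use the same equipment. The allocation must be available in the procedure room. Results would apply to patients in whom the catheter can be placed. At an assumed 5% to 10% failure, about 131 to 138 patients must start the procedure to randomise 124. The planned 62 per group need not change.
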